7.4 Serious Adverse Events

A serious adverse event (SAE) is any AE that:

- Results in death
- Is immediately life-threatening
- Requires inpatient hospitalization or prolongation of existing hospitalization
- Results in persistent or significant disability/incapacity
- Is a congenital anomaly/birth defect in offspring of the subject
- Is an important medical event that may jeopardize the subject or may require medical intervention to prevent one of the outcomes listed above

Medical or scientific judgment should be exercised in deciding whether expedited reporting is appropriate in this situation. Examples of medically important events are intensive treatment in an emergency room or at home for allergic bronchospasm, blood dyscrasias, or convulsions that do not result in hospitalizations; or development of drug dependency or drug abuse.

7.5 Time Period for Collection of Adverse Events

Adverse events will be collected from the time treatment, , throughout the treatment period and including the follow-up period of 30 days after the last dose of durvalumab and tremelimumab, or at the start of a new treatment

Serious adverse events will be recorded from the time treatment through30 days after the last dose of durvalumab and tremelimumab or the start of new treatment.

7.6 **Post-Study Events**

After the subject has been permanently withdrawn from the study, there is no obligation for the investigator to actively report information on new AEs or SAEs occurring in former study subjects after the 90-day safety follow-up period. However, if an investigator learns of any SAEs, including death, at any time after the subject has been permanently withdrawn from study, and he/she considers there is a reasonable possibility that the event is related to the investigator and product, the investigator should notify the Overall PI and AstraZeneca or its

representative.

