7.7 Follow-up of Unresolved Adverse Events

Any AEs that are unresolved at the subject's last AE assessment or other assessment/visit as appropriate in the study are to be followed by the investigator for as long as medically indicated, but without further recording in the eCRF. AstraZeneca retains the right to request additional information for any subject with ongoing AE(s)/SAE(s) at the end of the study, if judged necessary. After 90 days, only subjects with ongoing investigational product-related SAEs will continue to be followed for safety.

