7.8 Reporting of Serious Adverse Events to AstraZeneca

Investigators must report to the Overall PI any serious adverse event (SAE) that occurs after the initial dose of study treatment.

The Overall PI is responsible for reporting certain SAEs as expedited safety reports to applicable regulatory authorities, ethics committees, and participating investigators, in accordance with ICH guidelines and/or local regulatory requirements. The Overall PI may be required to report certain SAEs to regulatory authorities within 7 calendar days of being notified about the event; therefore, it is important that investigators submit additional information requested by the Overall PI or AstraZeneca/MedImmune as soon as it becomes available.

Investigators should provide all available information at the time of SAE Report Form completion. Investigators should not wait to collect additional information to fully document the event before notifying the Overall PI and MedImmune Patient Safety of an SAE. When additional information becomes available, investigators should submit a follow-up SAE Report Form (separate from the initial report form) with the new information. Any follow-up information to an SAE also needs to be provided to both the Overall PI and MedImmune Patient Safety within 24 hours of learning of the new information.

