7.9.4 Pneumonitis

Adverse events of pneumonitis are required to be reported within 24 hours of knowledge of the event to the Overall PI and MedImmune Patient Safety or designee using the Safety Fax Notification Form (see Section 7.9 for contact information).

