7.10 Expedited Adverse Event Reporting

7.10.1 Investigators **must** report to the Overall PI any serious adverse event (SAE) that occurs after informed consent, during treatment, or within 90 days of the last dose of treatment on the local institutional SAE form.

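### Section 7.5 stops SAE recording 30 days after the last dose or at new treatment, while 7.10.1 requires SAE reports to 90 days with no such stop

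*Combined protocol and SAP*

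**What the plan says.** Section 7.5 is the protocol's statement of the collection window. For adverse events in general it covers the treatment period, "including the follow-up period of 30 days after the last dose of durvalumab and tremelimumab, or at the start of a new treatment". For SAEs it reads "Serious adverse events will be recorded from the time treatment through30 days after the last dose", again with the start of new treatment as the alternative end. Words appear to be missing where each sentence gives its start, so nothing here rests on the start. The 30-day end is legible in both.

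Section 7.10.1, under the heading on expedited reporting, obliges investigators to report to the Overall PI any SAE that "occurs after informed consent, during treatment, or within 90 days of the last dose of treatment". It does not mention new treatment.

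Section 7.13 sends all adverse events to the toxicity case report forms through routine data submission. It adds that events which went through an expedited process must appear there as well. It gives no dates.

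Section 7.6 says that, once a subject is permanently withdrawn, the investigator need not actively "report information on new AEs or SAEs occurring in former study subjects after the 90-day safety follow-up period".

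Safety and tolerability is a secondary measure (13.1). Section 13.3 puts every participant who received study drug in the toxicity analysis, and 13.4.1 starts evaluability at the first dose. Neither says when it ends.

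**The concern.** For the same class of event, the protocol gives two different last days. A data manager working from 7.5 would close SAE recording at day 30, or earlier if new therapy starts. An investigator working from 7.10.1 would go on reporting to day 90. An SAE on day 60 would then be reported but, under 7.5, not recorded.

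What is at stake is the completeness and consistency of the SAE data behind the secondary safety endpoint. Both agents are immune checkpoint inhibitors. The protocol's own background (2.4.2) reports a Grade 5 neuromuscular disorder, considered related to this combination, 42 days after the last durvalumab dose. Days 31 to 90 can therefore contain events that a reader of the safety results would want counted.

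**Working it through.** The plan states no figure to reproduce. The check sets the sections side by side and takes the difference between the limits.

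| Section | Events covered | Stated end | Stop at new treatment? |
|---|---|---|---|
| 7.5, first sentence | AEs | 30 days after last dose | Yes |
| 7.5, second sentence | SAEs | 30 days after last dose | Yes |
| 7.10.1 | SAEs only | 90 days after last dose | Not mentioned |
| 7.6 | New AEs or SAEs in former subjects | Duty lifted after a 90-day follow-up | Not mentioned |
| 7.8 | SAEs | None given | Not mentioned |
| 7.13 | All AEs, and expedited ones again | None given | Not mentioned |
| 13.3, 13.4.1 | Toxicity analysis | None given | Not mentioned |

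**Step 1: the gap for SAEs.** Read the two end points in 7.5 as whichever comes first, and let t be the day after the last dose on which new treatment starts. The gap is 90 − min(30, t).
- New treatment on day 30 or later, or never: 90 − 30 = 60 days (days 31 to 90).
- New treatment before day 30: 90 − t, which rises towards 90 days as t approaches 0.

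**Step 2: can the sections be read together?** Suppose 7.5 governs the database and 7.10.1 governs safety reporting. An SAE on day 60 is outside 7.5 and inside 7.10.1, so it is reported. Section 7.13 then requires an event reported through an expedited process to appear in the routine data, which 7.5 closed on day 30. The two readings meet in the same data set and disagree.

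**Step 3: the background event.** Day 42 is 42 − 30 = 12 days past the 7.5 limit and 90 − 42 = 48 days inside the 7.10.1 limit. The dose cohort is not stated. The event shows that the period is not empty; no rate is inferred from it.

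**Step 4: weight of one participant.** If every enrolled participant is treated, one participant whose only SAE of a given type falls in the gap changes its reported rate by:
- 1/40 = 2.5 percentage points at the full sample size (13.2);
- 1/19 = 5.3 percentage points if the trial stops after stage 1 (Section 13).

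How many such participants there would be cannot be worked out from the documents.

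**The case against.** **Late SAEs would still be reported.** This is largely right. Section 7.8 asks for "any serious adverse event (SAE) that occurs after the initial dose of study treatment" and sets no end. For pneumonitis, 7.9.4 says "Adverse events of pneumonitis are required to be reported within 24 hours of knowledge of the event to the Overall PI", also without an end. Section 7.6 asks for notice of possibly related events "if an investigator learns of any SAEs, including death, at any time after the subject has been permanently withdrawn from study". Section 5.7 follows participants until death, so a late death would be known. A reader might infer that late SAEs go unreported; the documents do not support that. But reporting and recording are different things here: 7.7 has unresolved events followed "but without further recording in the eCRF". A death known from survival follow-up also does not supply a graded, attributed toxicity record.

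**Section 7.13 already brings late SAEs into the data.** In part it does, and that is why 7.5 conflicts with it. The route may also be narrower than it looks. Section 7.3 limits expedited reporting of listed events to those that differ from expectation, and 7.13 names the IRB and FDA as its examples. That makes 7.13 a less complete remedy for the 7.5 cut-off.

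**Non-serious events.** A reader might infer an equally firm 30- versus 90-day conflict for them. It is not established. Section 7.10.1 covers SAEs only, and 7.7 concerns events already open. Section 7.6 only lifts a duty after 90 days, for subjects withdrawn from the study. Under 5.8 that would not cover ordinary off-treatment participants, although Section 6 uses the phrase more loosely. The objection stands to this extent: 7.6 suggests a mismatch and no more.

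**A third window in 7.13, or a harmful difference in start points.** Neither is supported. Section 7.13 is silent on time and reads naturally as covering whatever 7.5 collects. Sections 7.8 and 7.10.1 do start SAE reporting at different points (first dose and consent), but 13.4.1 starts toxicity evaluability at first dose, so the toxicity analysis is unaffected.

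**Missing text.** Study calendar footnote J mentions 90 days but is cut off in the text available. It might say which window governs. No weight is placed on it.

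**Limited impact.** With a single arm there is no between-arm bias, and the primary analysis is untouched. Both points stand and limit the weight of this one.

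**Conclusion.** The inconsistency is real and confined to SAEs. The end of SAE recording in 7.5 and the end of SAE reporting in 7.10.1 differ by 60 days, or by up to 90 if new treatment starts soon after the last dose. Section 7.13 prevents the two from being treated as separate systems. If 7.5 is applied as written, SAEs in that period stay out of the recorded toxicity data, and Section 13 does not say which window the analysis uses.

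This rests on two readings: that the end points in 7.5 mean whichever comes first, and that a report under 7.10.1 counts as an expedited process for 7.13, as its section heading indicates. For non-serious events the mismatch is possible but unproven.

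The point should be fixed because it affects a secondary endpoint and the fix is cheap. It does not bear on the response rate, the sample size or the two-stage stopping rule, and no number of missed events is projected.

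**What to change.** 1. In 7.5, extend SAE recording to 90 days after the last dose, as 7.10.1 already requires for reporting, and remove the stop at new treatment for SAEs.
2. Flag on the case report form any SAE that begins after new therapy starts, so that it can be tabulated separately.
3. In 13.3 or 13.4.1, state that the toxicity analysis uses this window for SAEs.
4. Make the non-serious AE window in 7.5 and the 90-day wording in 7.6 consistent. The length is the sponsor's choice; the documents do not settle it.
5. Check that the full text of calendar footnote J agrees with the result.

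The cost is a protocol amendment, a change to the case report form window, and slightly more SAE data collection over days 31 to 90. Late events, above all those after new therapy, are harder to attribute, which is the reason for the flag.

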7.7 Follow-up of Unresolved Adverse Events

Any AEs that are unresolved at the subject's last AE assessment or other assessment/visit as appropriate in the study are to be followed by the investigator for as long as medically indicated, but without further recording in the eCRF. AstraZeneca retains the right to request additional information for any subject with ongoing AE(s)/SAE(s) at the end of the study, if judged necessary. After 90 days, only subjects with ongoing investigational product-related SAEs will continue to be followed for safety.

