2.4.2 Durvalumab and Tremelimumab Safety

A total of 102 subjects with advanced NSCLC have been treated with durvalumab and tremelimumab across 10 dose cohorts in Study D4190C00006. Across all dose cohorts, 95 of 102 subjects (93.1%) reported at least 1 AE (regardless of causality). AEs (all grades) reported in >10% subjects in decreasing order of frequency were diarrhea, fatigue, nausea, dyspnea, pruritus, rash, increased amylase, decreased appetite, pyrexia, increased ALT, cough, colitis, and increased lipase. All subjects in the tremelimumab 3 and 10 mg/kg dose cohorts experienced AEs; subjects in the durvalumab 20 mg/kg and tremelimumab 1 mg/kg Q4W cohort experienced the lowest AE rate (14 of 18 subjects, 77.8%).

Thirty-one of 102 subjects (30.4%) experienced AEs that were Grade 1 or 2 in severity. These events were manageable by general treatment guidelines. Grade 3 or higher AEs were reported in 64 of 102 subjects (62.7%). These events occurring in > 5% of subjects were colitis (8.8%), diarrhea (8.8%), and increased lipase (5.9%). In addition, \geq Grade 3 events that were uncoded as of the data cut-off date were verbatim terms (VTs) of gastrohepatic mass resection, elective diagnostic surgical excision of cerebral lesion, and chest pain (all Grade 3 and not related to study treatment); disease progression in 3 subjects (Grade 5 and not related to study treatment); and Grade 5 neuromuscular disorder occurring 42 days after the last dose of durvalumab and considered related to study treatment.

Treatment-related AEs were reported in 74 of 102 subjects (73%). Of these subjects, 12 had Grade 1, 21 had Grade 2, 35 had Grade 3, 4 had Grade 4, and 2 had Grade 5 events as maximum severity. The treatment-related Grade 5 events were polymyositis and an uncoded event of neuromuscular disorder (VT). Treatment-related Grade 3 or higher events that occurred in 2 or more subjects were colitis (9 subjects); diarrhea (8 subjects); increased lipase (6 subjects); increased AST, and pneumonitis (4 subjects each); increased ALT and increased GGT (3 subjects each); and increased amylase, anemia, and increased blood alkaline phosphatase (2 subjects each). Safety data from the durvalumab 15 and 20 mg/kg Q4W cohorts demonstrated a numerical increase in the frequency of treatment-related AEs and AEs leading to discontinuation of investigational product with increasing doses (> 1 mg/kg) of tremelimumab.

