			Once improving, gradually taper steroids over ≥28 days and consider prophylactic antibiotics, antifungals and in particular, anti PCP treatment (please refer to current NCCN guidelines for treatment of cancer- related infections (Category 2B recommendation) ⁴⁵ .	
			Consider pulmonary and infectious disease consult.	
			Consider as necessary discussing with Overall PI.	
	\geq Grade 3	Permanently discontinue study drug/study regimen.	Promptly initiate empiric IV methylprednisolone 1 to 4 mg/kg/day or equivalent.	
			Obtain pulmonary and infectious disease consults as clinically indicated.	
			Hospitalize the patient as clinically appropriate.	
			Provide supportive care (oxygen,	

Table 3: Dosi	Table 3: Dosing Modification and Toxicity Management Guidelines for Specific Immune- mediated Adverse Reactions			
Toxicity	Grade of the Event (NCI CTCAE version 4.03)	Dose Modifications	Toxicity Management	
			etc.). If no improvement within 5 days, additional work-up should be considered and prompt treatment with additional immunosuppressive therapy such as TNF inhibitors (e.g. infliximab at 5mg/kg every 2 weeks dose or equivalent) started. Caution: rule out sepsis and refer to infliximab label for general guidance before using infliximab. Once improving, gradually taper steroids over ≥28 days and consider prophylactic antibiotics, antifungals and in particular, anti PCP treatment (please refer to current NCCN guidelines for treatment of cancer- related infections (Category 2B recommendation) ⁴⁵ .	
Diarrhea / Enterocolitis	diarrhea/e such as in perforation Patients s (e.g., dise clostridiu Steroids s	cipants should be monitored for symptoms that may be related to enterocolitis (abdominal pain, cramping, or changes in bowel habits increased frequency over baseline or blood in stool) or related to bowel on (such as sepsis, peritoneal signs, and ileus). should be thoroughly evaluated to rule out any alternative etiology ease progression, other medications, infections including testing for um difficile toxin, etc.) should be considered in the absence of clear alternative etiology, even grade events, in order to prevent potential progression to higher grade		

Table 3: Dos	sing Modifi	cation and Toxicity Manag mediated Adverse F	ement Guidelines for Specific Immune- Reactions
Toxicity	Grade of the Event (NCI CTCAE version 4.03)	Dose Modifications	Toxicity Management
	Use analg peritoniti		sk symptoms of perforation and

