7.13 Routine Adverse Event Reporting

All Adverse Events **must** be reported in routine study data submissions to the Overall PI on the toxicity case report forms. **AEs reported through expedited processes (e.g., reported to the IRB, FDA, etc.) must** also be reported in routine study data submissions.

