C. D.	Section 9.1. Off points should be Vital signs to con time of vital sign Albumin, alkalin amylase, lipase, s	study bio followed nsist of he s should e phospha and TSH.	psy should t from C1D1 eart rate, resp be recorded) atase, total b	be collected p regardless of biratory rate, . May be rep ilirubin, bica	rior to the initiati drug holds or de blood pressure, to eated as clinically rbonate, BUN, ca	on of another ant elays. emperature, and o y indicated. alcium, chloride,	icancer treatment oxygen saturation creatinine, glucos	cation administration) and cycle 2 day 8, and t whenever feasible, or within 60 days of the (O ₂ sat). On infusion days, vital signs are to se, LDH, phosphorus, potassium, total prote	e last dose of stud o be collected an in, SGOT [AST]	ly medication. Biopsy time ytime pre-infusion (exact , SGPT [ALT], sodium,
E.	E. Triplicate EKG to be performed at baseline. EKGs should be obtained after participant has been resting for a minimum of 5 minutes. Each EKG of the triplicate should be separated by at least one minute and not more than 5 minutes. Subsequent EKGs to be performed as clinically indicated.									
F.										
G.										
H.								clinic schedule, or holidays.		
I.								e weather, vacations, clinic schedule, or hol	idays.	
J.								during the 90 days following the end of stu		
								. This follow up will be performed by revie		

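### Section 7.7 bars eCRF recording after the last AE assessment, so the later outcome and worst grade of non-serious related events still open at that point are lost

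*Combined protocol and SAP*

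**What the plan says.** Section 7.7 covers events already recorded. If unresolved at the subject's last AE assessment, or at another suitable visit, they are "followed by the investigator for as long as medically indicated, but without further recording in the eCRF". The company may ask for more information on ongoing events. After 90 days, safety follow-up continues only for ongoing product-related SAEs.

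The sections that would fix the date of the last AE assessment differ:

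- Section 7.5 collects AEs throughout treatment, "including the follow-up period of 30 days after the last dose of durvalumab and tremelimumab", or until a new treatment starts. It gives SAEs the same 30-day end.
- Section 7.6 ends the duty to report new events "after the 90-day safety follow-up period".
- Section 7.10.1 requires SAEs to be reported if they occur "within 90 days of the last dose of treatment on the local institutional SAE form".
- A study calendar footnote includes the words "during the 90 days following the end of". The rest of the footnote and the AE row of the calendar are damaged in the extracted text, so they cannot settle the timing.

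Serious events have further provisions: follow-up SAE report forms (7.8), notification of late related SAEs (7.6), and the rule that events sent through expedited channels must also "be reported in routine study data submissions" (7.13).

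Section 13.3 grades toxicity by CTCAE v4.03 and treats it as categorical data. It states no analysis of duration, resolution or reversibility.

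**The concern.** Safety and tolerability is a secondary objective (section 1.3). Two things about an immune-related event matter to a reader of the safety results: how bad it became and whether it went away. Section 7.7 has the investigator find out both, then keeps the answer out of the database.

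The rule may also fall unevenly. An event that ends treatment starts near the last dose and so has the least recording time left. Section 6.1 attaches a long steroid taper to most of these toxicities: "Once improving, gradually taper steroids over ≥28 days". An event still open when recording stops stays listed as ongoing at its current grade. If it later resolves, reversibility is under-described. If a non-serious event later worsens without becoming serious, its worst grade is understated.

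**Working it through.** The plan gives no figure to reproduce. The check has three parts.

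**1. Which events lose information**

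| Event at the last AE assessment | Route for later information |
|---|---|
| Resolved | None needed; outcome already recorded |
| Open, serious | SAE follow-up forms (7.8); related SAEs followed past 90 days (7.7); expedited events also in routine data (7.13) |
| Open, non-serious, later becomes serious | Reportable as an SAE within the 90 days of 7.10.1; if related and learned of later, 7.6 |
| Open, non-serious, stays non-serious | No mandatory route for later outcome or grade; only the company's optional request (7.7) |

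The gap is the last row. Section 7.9 narrows it further: all pneumonitis is reported within 24 hours, and hepatic function abnormality of unknown or product-related cause is reported as an SAE.

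**2. How the cut-off drives the size**

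Inputs: 28-day cycle (5.1); taper of at least 28 days (6.1); cut-off W = 30 days (7.5) or 90 days (taking the period in 7.6 and 7.7 to run from the last dose, as in 7.10.1). Assumptions, not from the documents: onset uniform over days 0 to 28 after the last dose, and a fixed duration T from onset.

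An event is open at cut-off if onset + T > W, so

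share open = (28 − (W − T)) / 28, limited to 0–100%.

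| T (days) | W = 30 | W = 90 |
|---|---|---|
| 14 | (28 − 16)/28 = 43% | 0% |
| 28 | (28 − 2)/28 = 93% | 0% |
| 42 | 100% | 0% |
| 56 | 100% | 0% |
| 84 | 100% | (28 − 6)/28 = 79% |

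At W = 90 the share stays at zero until T exceeds 90 − 28 = 62 days. A 28-day taper finishes before cut-off only if it starts by day 2 (30 − 28) or day 62 (90 − 28). Taper length is only a rough proxy for event duration, because the taper begins once the event is already improving.

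**3. Events open at day 30 by the protocol's own triggers**

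This part needs no assumed T. In Table 3, several permanent stops are defined by non-resolution within 30 days: Grade 3 rash, Grade 3 neurotoxicity, and Grade 2 or 3 peripheral neuromotor syndromes. A hold that starts x ≥ 0 days after the last dose leaves such an event open at day x + 30, which is at or past the day-30 cut-off. In Table 4, a further stop applies if steroids cannot be reduced within 56 days of the last dose, which is past day 30 but before day 90.

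Two limits apply. Some of these events will be SAEs: Table 3 recommends hospitalisation for Grade 3 neuromotor events, and admission meets the seriousness definition in 7.4. Also, section 6 allows holds of up to 56 days. If the treatment period in 7.5 is read as running until the decision to stop, the last AE assessment could fall later than day 30.

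**The case against.** The strongest counter-case is that the rule affects little of what the trial plans to report. Ongoing at last assessment is an accurate, censored status, and section 13.3 promises no resolution analysis that could go wrong. Serious events are covered elsewhere. The percentages come from assumed onset and duration and fall from 93% to 0% for a 28-day event when the cut-off moves from day 30 to day 90. All of this stands, and it limits the point to non-serious events and mainly to description.

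A reader might infer four stronger things that the documents do not support:

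- **That every treatment-ending immune event is frozen.** Only events open at the last AE assessment are affected.
- **That about 10 of 40 patients are affected.** Section 2.4.2 reports 26 of 102 (25.5%) stopping because of SAEs, and 0.255 × 40 = 10.2. Those are serious events, some of them not immune-related (sepsis, tumour progression), so the figure does not size a non-serious gap.
- **That the "Grade 5 neuromuscular disorder occurring 42 days after the last dose of durvalumab and considered related to study treatment" in section 2.4.2 illustrates the loss.** A fatal event is an SAE, and its lateness concerns capture of new events, not the outcome of open ones.
- **That 7.7 contradicts 7.8 and 7.13.** Section 7.8 uses a separate form, and 7.13 requires events to be in routine data without addressing later updates. All three can be followed together, although the plan does not say how they fit.

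The objection also notes that following non-serious events until death would cost more than it first appears, since 7.7 itself narrows follow-up after 90 days. That is right, and the fix is bounded accordingly.

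**Conclusion.** The point holds in a limited form. Under section 7.7, a non-serious treatment-related event open at the last AE assessment keeps its ongoing status and its grade to date, and later resolution or worsening short of an SAE does not reach the database. The consequences are an incomplete account of reversibility and a possible understatement of worst grade in the CTCAE-based summary. To say that outcomes are missing from a planned resolution analysis would go too far, since none is planned.

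The number of patients cannot be derived from the documents. Under a day-30 cut-off the gap could include several events that end treatment because they did not resolve. Under a day-90 cut-off, with onset within 28 days of the last dose, it shrinks to events lasting more than 62 days. The 30-day and 90-day statements must therefore be reconciled before the size can be known. The primary endpoint is untouched. This is a cheap improvement to a secondary safety objective.

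**What to change.** In section 7.7, replace the bar on further eCRF recording with a requirement to update the existing AE row for each treatment-related event open at the last AE assessment: outcome, date of resolution or stabilisation, and worst grade reached. Apply it through the 90-day safety follow-up that the protocol already refers to, and beyond 90 days only for the related SAEs that 7.7 already follows. State that this is consistent with 7.8 and 7.13. Reconcile sections 7.5, 7.6, 7.7 and 7.10.1, and the calendar, so that the date of the last AE assessment is unambiguous. In section 13.3, say that worst grade and the proportion resolved will be reported from these fields.

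The cost is a short text change and a little extra data entry, using information the investigator is already told to follow. It adds no visits or procedures and leaves clinical management unchanged.
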